5.2 Variables Used for Stratification of Randomization

At Baseline, subjects were randomized in a 1:1:1:1:1:1 ratio to receive one of the six treatment groups (double-blind ABT-494 induction doses or matching placebo).

The following are the treatment groups:

Group 1: ABT-494 3 mg BID

Group 2: ABT-494 6 mg BID

Group 3: ABT-494 12 mg BID

Group 4: ABT-494 24 mg BID

Group 5: ABT-494 24 mg QD

Group 6: Placebo

The randomization at Baseline was stratified by endoscopic disease severity (SES-CD < 15 and \geq 15), prior anti-TNF use (naïve and experienced), and by participation in the substudy of the gene expression in intestinal biopsies (Yes and No). As part of the randomization at Baseline, subjects were randomly assigned (1:1) to have their follow-up ileocolonoscopy done at Week 12 or Week 16.

At Week 16, subjects who have completed the induction period were re-randomized in a ratio of 1:1:1 to one of the three double-blinded doses of ABT-494 3 mg BID, 6 mg BID or 12 mg BID. The re-randomization was stratified by dose received during the first 16 weeks, and overall response (responder versus non-responder) at Week 16. The subjects who were re-randomized at Week 16 to ABT-494 24 mg QD prior to Protocol Amendment 2 continued to receive the same double-blind dose until Week 52/PD.

Overall response consists of both Endoscopic response and Clinical response. The central reader endoscopic score will be used for calculating the Endoscopic response for the evaluation of the efficacy endpoints. However, for stratification re-randomization, the endoscopic score at baseline from central reader and the endoscopic score at Week 12 or Week 16 from site local reader will be used in order to determine response status.

6.0 Analysis Conventions

Definition of Baseline for Induction Period

The Baseline visit date for Induction Period is the date when the first dose of study drug is received and referred to as Day 1 or Week 0. The Baseline value for a variable is defined as the last non-missing value on or before the date of the first dose of study drug for Induction Period.

Definition of Baseline for Extension Phase

The Baseline visit date for Extension Phase is the date when the first dose of study drug for Extension Phase is received and referred to as Day 1 or Week 0 of Extension Phase. The Baseline value for a variable is defined as the last non-missing value on or before the date of the first dose of study drug for Extension Phase.

Definition of Rx Days (Days Relative to the First Dose of Study Drug)

Rx Days are calculated for each time point of interest and it provides a quantitative measure of days between the event and the first dose date. That is, the Rx Day is calculated as the event date minus the date of first dose of study drug plus 1.

The Rx Day will be a negative value when the time point of interest is prior to the date of first dose of study drug, and the Rx Day will be a positive value when the time point of interest is after the first dose date. By this calculation algorithm the first dose day is Rx Day 1, while the day prior to the date of first dose is defined as Rx Day –1 (there is no Rx Day 0). Rx Days are used to map actual study visits to the protocol specified study visits.

Dealing with Multiple Measurements Collected on the Same Day

For efficacy related analyses other than imaging endpoints, if multiple measurements for a particular parameter are collected on the same day for the same subject, the average of those measurements will be used.

For safety related analyses, if multiple measurements are made for a particular laboratory or vital sign parameter on the same day for the same subjects, the average of the values will be used in the analyses of change from Baseline. For summaries and listings for shift from baseline and potentially significant values, all collected values within the pre-specified treatment window will be used.

Definition of Analysis Windows

Since subjects do not always adhere to the study visit schedule, the following rules will be applied to assign actual visits to protocol-specified visits including early termination visits. For each study visit mentioned in the protocol, a nominal or target day will be selected to represent the corresponding visit along with a window around the target day. Windows will be selected in a non-overlapping fashion so that a date collected on the CRF does not correspond to multiple visit windows. Moreover, windows will not discard any Post-Baseline measurement recorded on the CRF. If a subject had two or more actual visits in one visit window, the visit closest to the schedule visit will be used as the study visit for that window. If two visits are equidistant from the target, then the later visit will be used for reporting.

Table 2. Visit Windows for Analysis of CDAI and CRP, Laboratory Parameters and Vital Signs for 36-Week Double-Blind Extension Phase

| Scheduled Week | Nominal Day | Time Window (Rx Day Range) |
|--------------------------------------|----------------|-------------------------------|
| Week 0 (Baseline of Extension Phase) | 1 ^a | ≤ 1 |
| Week 4 (Week 20 of the study) | 29 | 2 – 57 |
| Week 12 (Week 28 of the study) | 85 | 58 – 113 |
| Week 20 (Week 36 of the study) | 141 | 114 – 169 |
| Week 28 (Week 44 of the study) | 197 | 170 – 225 |
| Week 36 (Week 52 of the study) | 253 | 226 – 999 |

Rx Day B = date of visit – date of first study drug in double-blind extension phase + 1

a. Day of first dose of study drug in double-blind extension phase.

Table 3. Visit Windows for Analysis of SES-CD, EIM, IBDQ, EQ5D, and WPAI for 36-Week Double-Blind Extension Phase

| Scheduled Week | Nominal Day | Time Window (Rx Day Range) |
|--------------------------------------|--------------------|---------------------------------------|
| Week 0 (baseline of Extension Phase) | 1 ^a | ≤ 1 |
| Week 36 (Week 52 of the study) | 253 | 2 – 999 |

Rx Day B = date of visit – date of first study drug in double-blind extension phase + 1

a. Day of first dose of study drug in double-blind extension phase.

Table 4. Visit Windows for Analysis of Bristol Stool Chart and Fecal Calprotectin for 36-Week Double-Blind Extension Phase

| Scheduled Week | Nominal Day | Time Window (Rx Day Range) |
|--------------------------------------|--------------------|---------------------------------------|
| Week 0 (baseline of Extension Phase) | 1 ^a | ≤ 1 |
| Week 12 (Week 28 of the study) | 85 | 2 – 169 |
| Week 36 (Week 52 of the study) | 253 | 170 – 999 |

Rx Day B = date of visit – date of first study drug in double-blind extension phase + 1

a. Day of first dose of study drug in double-blind extension phase.

CD-Related Corticosteroid Use

Subjects not on CD-related corticosteroids (systemic or rectal corticosteroids) at Induction Baseline which are then initiated during the study or who have dosages of these medications increased to greater than the dose taken at Baseline will be censored for efficacy assessments (i.e., will be considered non-responders for categorical endpoints and will have Baseline values carried forward for non-categorical assessments) from that point through the end of the study. These subjects will continue to be evaluated in the safety population.

The equivalent steroid dose will be determined based on the table below:

| Corticosteroid | Equivalent Dose (mg) |
|--------------------|----------------------|
| Cortisone | 25 |
| Hydrocortisone | 20 |
| Prednisone | 5 |
| Prednisolone | 5 |
| Triamcinolone | 4.0 |
| Methylprednisolone | 4.0 |
| Betamethasone | 0.75 |
| Dexamethasone | 0.75 |
| Budesonide | 1 |
| Beclomethasone | 5 |
| Beclometasone | 5 |

Open-Label Therapy

Subjects who are considered by the investigator to have not achieved meaningful symptomatic relief and have met the criteria for inadequate response at or after Week 20 of the study (Week 4 of the Extension Phase) will be eligible to receive open-label therapy with ABT-494 12 mg BID. These subjects will be censored for efficacy assessments (i.e., will be considered non-responders for categorical endpoints and will have the non-missing value prior to open-label therapy carried forward for non-categorical assessments) from that point through the end of the study.

Definition of Missing Data Imputation

The following imputation methods will be used to impute missing values in the efficacy analyses. In addition, an observed case analysis will be performed.

Non-Responder Imputation (NRI)

The NRI approach is used for binary efficacy variables. These variables can take values of 'Achieved' or 'Not Achieved' or may be missing for any reason including discontinuation from study. According to the NRI imputation approach, all missing values will be considered as 'Not Achieved.'

Last Observation Carried Forward (LOCF)

For all variables (categorical variables and continuous variables), the following rules will be used for the LOCF approach:

1. Extension Baseline and Pre-Baseline values will not be used to impute the missing Post-Baseline values.
2. Missing values after Study Day 1 will be imputed using the latest non-missing values after Day 1 and prior to the missing value. If there are no non-missing values after Baseline, then the LOCF value will be missing.

Observed Case (OC)

Observed case analysis will be performed such that missing values will not be imputed. However, all observed values will be replaced by Induction Baseline value once subjects received CD-related corticosteroid therapy, or value prior to open label therapy once subjects moved to open-label therapy.

Mixed-Effect Model Repeated Measure (MMRM)

The MMRM model will be used for continuous efficacy variables with longitudinal data as the primary analysis. The MMRM model includes the baseline values as covariate, treatment, time point and treatment-by-time point interaction as fixed effects; and subjects within treatment as random effect. An unstructured (co)variance structure will be used to model the within-subject error. The comparison at a time point will be the contrast between treatments at that time point. Satterthwaite's approximation will be used to estimate denominator degrees of freedom.

Imputation of Missing Dates

For Baseline, efficacy, and safety parameters, if the day and/or month are missing, the following conventions will be used to impute the missing dates:

- 01 for missing start day

- End of month for missing end day
- January 1st for missing start month
- December 31st for missing end month

In case of partially missing AE start and stop dates, the dates will be imputed by comparing to first dose date of study medication so that the corresponding AEs will be made treatment-emergent whenever possible. If the start date of an AE is partially missing and the month is the same as the start date of a new therapy, the AE will be made treatment emergent to the new therapy.

In case of missing or partially missing study drug dosing dates, the dates will not be imputed. Subjects will be treated as not receiving dose on that date.

Rule for CDAI Calculation

Up to 14 days of diary entries will be evaluated from the ePRO tool for the CDAI calculation for each visit. The diary entries on the days the subjects receive endoscopy preparation medications, the day of endoscopy procedure, and 2 days after endoscopy procedure will be excluded. For each CDAI subscore, the available scores from the most recent diary days (at least 4 days, up to 7 days) prior to actual day of the study visit will be summed, and then multiplied by the corresponding multiplier to get subtotal score. If available diary entries are fewer than 7 days, the subtotal score will be calculated as (summed total available score/number of days) \times 7 \times corresponding multiplier. The three subtotal scores that are based on ePRO (number of liquid/very soft stools, abdominal pain rating, and general well-being) will then be rounded to one decimal. The final CDAI is rounded to a whole number.

If a subject has less than 4 days of diary data, the total CDAI score will not be calculated and will be considered missing.

Same rule will be applied to average daily stool frequency and average daily abdominal pain.

Bristol Stool Chart

Up to 14 days of diary entries will be evaluated from the ePRO tool for the Bristol Stool Chart calculation. These assessments on the day of endoscopy procedure, the day before endoscopy procedure (due to preparation medications), and 2 days after endoscopy procedure are excluded. The 7 most recent non-missing assessments will be used for the analysis. The Bristol Stool Chart is calculated as the number of days the subjects with Type 6 or Type 7 divided by the total number days with non-missing assessments, rounded to two decimal.

If a subject has less than 4 days of diary data, the Bristol Stool Chart will not be calculated and will be considered missing.

If a subject achieved reduction from Baseline $\geq 50\%$, this subject will be classified as Responder.

SES-CD Scoring

All colonoscopies shall be performed and recorded in video format. To be eligible for the study, the screening colonoscopy may be performed during the Screening Period (or up to 45 days before the Baseline visit if Amendment 2 is in place at the site). Colonoscopies will also be performed at the Week 12/16 visit and Week 52 visit. Investigators shall provide their SES-CD score assessment on the SES-CD score sheet for the baseline, Week 12/16 visit and Week 52 visit. The investigator SES-CD scores are to be entered in the appropriate eCRF, however neither the Investigator's Baseline, nor Week 12/16, Week 52 SES-CD scores will be used for the study's efficacy analyses unless the adjudicator agree with the site reading.

All videotaped colonoscopies will undergo central review. One primary central reviewer will evaluate the videotaped colonoscopies and provide the SES-CD scores to Parexel. A second central reviewer will adjudicate between the investigator's and the central reviewer's SES-CD scores if there is discrepancy (more than 10% difference) in total SES-CD score. The adjudicator will select the final SES-CD score that he/she most

agrees with from those provided by the investigator and the central reviewer, and this final SES-CD score will be entered into the study database and be used for the study's efficacy analyses. If there is no discrepancy between the investigator and the central reviewer, that central reviewer's score will be entered into the study database and serve as the SES-CD score to be used for the study's efficacy analyses.

If there is a missing SES-CD individual variable in the SES-CD score for the study's efficacy analyses (for all variables except the "Presence of Narrowing" variable), the following imputation rules will be applied:

If the same individual variable is:

- Missing at Week 52 but present at Week 12/16: the missing Week 52 value will be imputed based on the value at Week 12/16.
- Missing at Week 52 but no endoscopy performed at Week 12/16: the missing Week 52 value will be imputed based on the value at Induction Baseline.

If there is a missing SES-CD "Presence of Narrowing" individual variable in the SES-CD score for the study's efficacy analyses, the following imputation rules will be applied:

If the Presence of Narrowing individual variable is:

- Missing at Week 52 but present at Week 12/16: the missing Week 52 value will be imputed based on score at Week 12/16.

However, if a Week 52 individual variable is scored for intestinal segments proximal to (above) the segment with the missing Presence of Narrowing variable, the maximum imputed value for the missing Presence of Narrowing individual variable will be 2.

- Missing at Week 52 but no endoscopy performed at Week 12/16: the missing Week 52 value will be imputed based on score at Induction Baseline.

However, if a Week 52 individual variable is scored for intestinal segments proximal to (above) the segment with the missing Presence of Narrowing

variable, the maximum imputed value for the missing Presence of Narrowing individual variable will be 2.

(Gastrointestinal anatomy places the ileum proximal to the right colon, which is proximal to the transverse colon, which is proximal to the sigmoid and left colon, which is proximal to the rectum.)

A sensitivity analysis (Worst Case Imputation) will be performed by imputing all missing Induction Baseline individual variables as '0' and all missing Week 52 variables as '3' except the Week 52 Presence of Narrowing individual variable. At Week 52, the worst values for Presence of Narrowing individual variable will be 2 for Rectum, Sigmoid and Left Colon, Transverse Colon, and Right Colon, and 3 for Ileum.

Isolated Ileal Crohn's Disease at Induction Baseline

Isolated Ileal Crohn's disease at Induction Baseline is defined as all individual variables for Rectum, Sigmoid and Left Colon, Transverse Colon, and Right Colon are zero at Induction Baseline and subscore for ileal ≥ 4 . If any of the individual variables is missing or not zero, this subject is classified as Not Isolated Ileal Crohn's disease at Induction Baseline.

Definition of Endoscopic Remission

SES-CD ≤ 4 and at least two point reduction versus Induction baseline and no subscore > 1 in any individual variable.

Definition of Endoscopic Response

SES-CD at least 25% reduction from Induction baseline.

Definition of Enhanced Endoscopic Response

SES-CD reduction from Induction baseline $> 50\%$ (or for an Induction Baseline SES-CD of 4, at least a 2 point reduction from Induction Baseline).

Definition of Endoscopic Improvement

SES-CD reduction from Induction baseline $> 50\%$ or endoscopic remission.

Definition of Endoscopic Healing

SES-CD ulcerated surface subscore of 0 in subjects with SES-CD ulcerated surface subscore ≥ 1 at Induction Baseline.

Definition of Clinical Remission

Average daily stool frequency ≤ 1.5 and not worse than Induction baseline AND average daily abdominal pain ≤ 1.0 and not worse than Induction baseline.

Definition of Clinical Response

Average daily stool frequency at least 30% reduction from Induction baseline and average daily abdominal pain not worse than Induction baseline OR average daily abdominal pain at least 30% reduction from Induction baseline and average daily stool frequency not worse than Induction baseline.

Definition of Modified Clinical Remission

Average daily stool frequency ≤ 2.8 and not worse than Induction baseline AND average daily abdominal pain ≤ 1.0 and not worse than Induction baseline. This endpoint will only be analyzed among subjects with Induction baseline average daily stool frequency ≥ 4 or average daily abdominal pain ≥ 2.0 .

Definition of Enhanced Clinical Response

Average daily stool frequency at least 60% reduction from Induction baseline and average daily abdominal pain not worse than Induction baseline OR average daily abdominal pain at least 35% reduction from Induction baseline and average daily stool frequency not worse than Induction baseline or modified clinical remission.

Definition of Remission

Remission at Week 52 is defined as both Endoscopic remission at Week 52 AND Clinical remission at Week 52.

Definition of Response

Response at Week 52 is defined as both Endoscopic response at Week 52 AND Clinical response at Week 52.

EuroQol-5D-5L (EQ-5D)

EQ-5D is a standardized measure of health status developed by the EuroQol Group in order to provide a simple, generic measure of health for clinical and economic appraisal. The EQ-5D consists of 2 pages. The first page measures 5 dimensions of the health status (mobility, self-care, usual activities, pain/discomfort, and anxiety/depression) with 5 levels per dimension (no problems, slight problems, moderate problems, severe problems, and unable corresponding to Level 1 to Level 5 respectively). The second page is an EQ Visual Analogue Scale (EQ VAS). EQ-5D health states, defined by the EQ-5D-5L descriptive system on the first page, may be converted into a single index value. The change from baseline of the index value and EQ VAS will be analyzed and reported. UK scoring algorithm will be used ([Table 5](#)).

Table 5. An EQ-5D-5L Value Set for England

| | Central Estimate | Value for Health State 23245 |
|--|---|------------------------------|
| Mobility | | |
| No Problem | 0 | |
| Slight | 0.051 | 0.051 |
| Moderate | 0.063 | |
| Severe | 0.212 | |
| Unable | 0.275 | |
| Self-Care | | |
| No Problem | 0 | |
| Slight | 0.057 | |
| Moderate | 0.076 | 0.076 |
| Severe | 0.181 | |
| Unable | 0.217 | |
| Usual Activities | | |
| No Problem | 0 | |
| Slight | 0.051 | 0.051 |
| Moderate | 0.067 | |
| Severe | 0.174 | |
| Unable | 0.190 | |
| Pain/Discomfort | | |
| No | 0 | |
| Slight | 0.060 | |
| Moderate | 0.075 | |
| Severe | 0.276 | 0.276 |
| Unable | 0.341 | |
| Anxiety/Depression | | |
| Not | 0 | |
| Slight | 0.079 | |
| Moderate | 0.104 | |
| Severe | 0.296 | |
| Unable | 0.301 | 0.301 |
| The value for health state 23245: 1 – 0.9675 × (sum of the subscores) | $1 - 0.9675 \times (0.051 + 0.076 + 0.051 + 0.276 + 0.301) = 0.270$ | |

The index value is $1 - 0.9675 \times$ sum of 5 components based on central estimates.

The minimum index value is – 0.281 (health state 55555), and the maximum index value is 1 (health state 11111).¹

If one of the 5 dimensions is missing, the EQ-5D index value will be missing.

7.0 Demographics, Baseline Characteristics, Medical History, and Previous/Concomitant Medications

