- Change from Induction Baseline in fecal calprotectin level over time.
- Change from Induction Baseline in hs-CRP at over time.
- Change from Induction Baseline in IBDQ at Week 52.
- Change from Induction Baseline in EQ-5D at Week 52.
- Change from Induction baseline in EIMs at Week 52.

- Proportion of subjects with isolated ileal Crohn's disease who achieve remission at Week 52.
- Proportion of subjects with isolated ileal Crohn's disease who achieve modified clinical remission at Week 52.

For categorical efficacy endpoints for double-blind extension phase, the pairwise comparisons for the difference in proportions of subjects between ABT-494 3 mg BID group and ABT-494 higher dose groups will be analyzed using the Chi-square test (or Fisher's exact test if $\geq 20\%$ of the cells have expected cell count < 5 .). Additionally, the 95% confidence interval based on normal approximation for the difference in proportions will be provided.

The non-responder imputation will be used for subjects with missing data at the endpoint evaluated. The last observation carried forward (LOCF) method will also be used as the sensitivity analyses.

In general, continuous efficacy variables with repeated measurements will be analyzed using a Mixed Effect Repeated Measure (MMRM) model. The mixed model includes the categorical fixed effects of treatment, week and treatment-by-week interaction and the continuous fixed covariates of Induction baseline measurement. An unstructured variance-covariance matrix will be used. If convergence is not achieved, other variance-covariance matrix will be explored until coverage. The parameter estimations will be based on assumption of data being missing at random and using the method of restrictive maximum likelihood (REML).

Continuous secondary efficacy variables will also be analyzed using an Analysis of Covariance (ANCOVA) model including factors for treatment group, and Induction Baseline values as a covariate. The MMRM analysis is considered primary for inferential purposes.

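### Extension SAP Table 3 lets an early-termination endoscopy stand as the Week 52 result, and no planned analysis shows the effect; separately and smaller, the Induction SAP omits the protocol's discontinuation rule for clinical remission

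*SAP*

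**What the plan says.** The SAP document holds two plans, called here the Extension SAP and the Induction SAP.

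**Extension SAP.** Section 6.0, Definition of Analysis Windows, assigns actual visits, ET visits included, to scheduled visits and adds that "windows will not discard any Post-Baseline measurement recorded on the CRF". Table 3 covers SES-CD, EIM, IBDQ, EQ-5D and WPAI. Its only post-baseline row is "Week 36 (Week 52 of the study) | 253 | 2 – 999". On missing data, Section 6.0 says: "According to the NRI imputation approach, all missing values will be considered as" Not Achieved. Section 10.2 repeats the scope: "The non-responder imputation will be used for subjects with missing data at the endpoint evaluated". Two events override an observed value: a switch to open-label drug, and a new or increased CD-related corticosteroid. Leaving the study does not.

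**Protocol, extension endoscopy.** Section 5.3.1.1 rules out an ET endoscopy for exits prior to Week 28. The Synopsis says one is not required for exits before or at Week 28. Section 5.3.1.1 also uses a pooled Week 52/ET label for the endoscopy that supplies the SES-CD subscores. It states an explicit substitution only for induction exits between Weeks 8 and 12, where the ET endoscopy becomes the Week 12 result.

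**Induction.** Protocol Sections 8.1.3 and 8.1.6.1.1 score any discontinuation before Week 16, whatever the reason, as not achieved for clinical remission. Induction SAP Section 10.2 applies NRI to missing stool frequency, abdominal pain or SES-CD and does not carry that rule over. Its Table 2 opens the Week 16 window at Rx Day 100, again with ET visits included. Nothing is entered under Section 12.1, the summary of changes from the protocol.

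**The concern.** The Week 52 endpoints in Extension SAP Section 10.2 read as status at Week 52, with subjects who lack a Week 52 assessment counted as failures. Under Table 3, a subject who stopped double-blind treatment months earlier can enter the numerator on the strength of the exit endoscopy. If such exits differ in number or reason between doses, the comparisons with 3 mg BID shift, and a reader of the results could not tell.

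The endpoints exposed are those that need endoscopy alone: endoscopic remission, response, enhanced response, improvement and healing, SES-CD ≤ 2, SES-CD = 0, and endoscopic remission after stopping corticosteroids.

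In induction the stake is narrower but touches a co-primary endpoint: the protocol and the SAP can score the same early leaver differently on clinical remission.

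**Working it through.** **1. The plan's own windows.** Nominal day = 7 × extension week + 1, so Week 28 of the study is 7 × 12 + 1 = 85 and Week 52 is 7 × 36 + 1 = 253. Cut-points are midpoints of adjacent nominal days. Table 2: (29 + 85)/2 = 57, (85 + 141)/2 = 113, (141 + 197)/2 = 169, (197 + 253)/2 = 225. Table 4: (85 + 253)/2 = 169. All match the printed limits.

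**2. Labels given to an ET visit.** The relevant rows are "Week 12 (Week 28 of the study) | 85 | 58 – 113" and "Week 36 (Week 52 of the study) | 253 | 226 – 999" in Table 2, and "Week 36 (Week 52 of the study) | 253 | 170 – 999" in Table 4.

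| Rx Day | Table 2 (CDAI, CRP) | Table 4 (calprotectin) | Table 3 (SES-CD) | Days before 253 |
|---|---|---|---|---|
| 85 | Week 28 | Week 28 | Week 52 | 168 |
| 141 | Week 36 | Week 28 | Week 52 | 112 |
| 197 | Week 44 | Week 52 | Week 52 | 56 |
| 226 | Week 52 | Week 52 | Week 52 | 27 |

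The earliest value accepted as Week 52 is 253 − 226 = 27 days early in Table 2 and 253 − 170 = 83 days early in Table 4. For SES-CD the bound comes from the protocol, not from Table 3: about Rx Day 85, so 253 − 85 = 168 days. This is approximate. The two protocol statements on Week 28 differ, and the ±7-day endoscopy window could stretch it to 253 − 78 = 175.

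**3. Do the planned analyses expose it?** Take a favourable ET endoscopy on Rx Day 85.
- NRI: the value is not missing, so it stays Achieved.
- LOCF: nothing is missing, so nothing is imputed. Nor is there an alternative to carry, since Table 3 has no earlier post-baseline slot and "Extension Baseline and Pre-Baseline values will not be used to impute the missing Post-Baseline values".
- Observed case: the value is observed and kept.
- Worst Case Imputation: only missing segment scores change; the ET examination is still the Week 52 one.

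**4. Size per subject.** With 210 randomised equally to six groups, 35 are on placebo, and the Extension SAP summarises induction-placebo subjects separately. If everyone else were re-randomised, a dose group would hold at most (210 − 35)/3 = 58.3, and one subject moves its rate by 1/58.3 = 1.7 points. Efficacy is analysed within ITT-R and ITT-NR, so the actual step is larger. As illustration, with an assumed 30–60% responders, ITT-R has 17.5 to 35 per dose and one subject moves it by 5.7 to 2.9 points.

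**5. Induction.** Week 16 is nominal Day 113. The ±3-day visit window makes Days 110–112 on schedule, so the clearly early part of the window is Rx Days 100–109. A leaver with an ET visit there and at least 4 usable diary days has non-missing scores and can be a success. One such subject moves a 35-subject arm by 1/35 = 2.9 points.

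**The case against.** The strongest defence is that Table 3 is deliberate. The protocol's Week 52/ET wording says which endoscopy supplies the score, and Table 3 can be read as implementing it. No protocol rule for the extension makes discontinuation a failure; protocol Section 8.1.6.2.1, like the SAP, applies NRI to missing data. This stands: a reader might infer that Table 3 breaches the protocol, and the documents do not support that. The pooled label, however, stops short of saying that an extension ET result is a Week 52 result, which the protocol does say for one kind of induction exit.

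A reader might also take the differing labels across Tables 2, 3 and 4 as a contradiction. They are not. CDAI and calprotectin have Week 28 visits; SES-CD has a single scheduled assessment in the extension, so no other label exists for it. The comparison shows only how much earlier a Week 52 SES-CD value may be.

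The affected group may be small. Inadequate responders can move to open-label drug from Week 20 and are then non-responders, and the extension analyses carry no multiplicity control. This also stands.

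For induction, the mixed-imputation sensitivity analysis in Section 10.2 already fails leavers for adverse events or lack of efficacy. On that group it is stricter than the primary analysis; leavers for other reasons remain uncovered. The SAP describes itself as elaborating the protocol, so its silence need not repeal the rule. The empty Section 12.1 is weak evidence, since the added quadratic model and the dropped anti-TNF stratification factor are not listed there either.

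**Conclusion.** The point holds as a gap in definition and in sensitivity analysis. As written, an early leaver with a favourable ET endoscopy counts as an endoscopic success at Week 52 up to about 168 days early, and none of the planned analyses shows how often or with what effect.

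The total effect is not known. The documents give no dropout figures, so a reader who infers materially inflated Week 52 rates goes further than they allow. What can be stated is the step per subject: at least about 1.7 points in a dose group of at most about 58.

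Nor does the finding extend equally to composite remission and response. These also need a Week 52 clinical result. If stool frequency and pain follow Table 2, which is an inference because no extension table names them, an exit before Rx Day 226 leaves the clinical part missing and the composite fails.

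The induction point is separate and smaller. The protocol and SAP texts differ for ET visits on about Rx Days 100–109. A reader might infer that the locked analysis misclassified subjects; the documents do not say whether the protocol rule was applied.

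**What to change.** **Extension SAP.**
- For the binary Week 52 endoscopic endpoints under NRI, score subjects who discontinued with their last endoscopy before a stated lower limit as Not Achieved. Rx Day 226, the Table 2 edge, is one choice. Scheduled endoscopies at 253 ± 7, that is Rx Days 246–260, are unaffected. Report the ET-as-Week-52 result as the sensitivity analysis.
- If the sponsor intends Table 3 as it stands, say so, report the Not Achieved version as the sensitivity analysis, and give the number of ET-derived values per dose group.
- Leave the IBDQ, EQ-5D and EIM windows alone, since removing observed ET values from their main analysis is not shown to reduce bias. Report how many of their Week 52 values come from ET visits.
- Reconcile the two protocol statements on ET endoscopy around Week 28.

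Cost: a few sentences and one derived flag on existing data. Reported Week 52 endoscopic rates may be slightly lower.

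**Induction SAP.** Apply the protocol's discontinuation rule in the primary analysis of clinical remission. If the analysis run after the December 2016 lock did not, record the departure with its reason in Section 12.1 and report the co-primary result with the rule applied. Cost: one re-run on existing data.
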